8.3 Serious Adverse Events

8.3.1 *Definition of Serious Adverse Event (SAE)*

In general, an SAE is any event that meets any of the following criteria listed below regardless of the relationship to study drug:

- Death
- Life-threatening
- Prolongation of existing hospitalization
- Persistent or significant disability/incapacity
- Congenital anomaly/birth defect in the offspring of a subject who received zavege pant
- Other: Important medical events such as admission to ICU because of worsening of subject's condition, intubation or other medical procedures performed because of worsening of subject's condition, etc.

- Other important medical events that may not result in death, be life-threatening, or require hospitalization, may be considered an SAE when, based upon appropriate medical judgment, they may jeopardize the subject and may require medical or surgical intervention to prevent one of the outcomes listed in this definition. Examples of such events are (but not limited to):
 - Intensive treatment in an emergency room or at home for allergic bronchospasm
 - Blood dyscrasias or convulsions that do not result in inpatient hospitalization
 - Development of drug dependency or drug abuse
 - Potential drug induced liver injury (see Section 8.3.5)
 - Abuse or Overdose of medication
- Potential study medication abuse (including cases of excessive non-compliance with study medication dosing instructions or subjects who discontinue treatment without returning study medication) should be documented in the source record and reported as an AE or SAE as appropriate. Investigators must monitor subjects for possible cases of abuse of study medication (subjects taking study drug for non-therapeutic purposes, e.g. for psychoactive effects such as high or euphoria). Investigators should obtain more information and explanation from subjects when there are study drug accountability discrepancies
- Potential study medication overdose is defined in Section 8.3.3

In general, hospitalization signifies that the subject has been detained (usually involving at least an overnight stay) at the hospital or emergency ward for observation and/or treatment that would not have been appropriate in the physician's office or outpatient setting. When in doubt as to whether 'hospitalization' occurred or was necessary, the AE should be considered serious.

The following hospitalizations are not considered SAEs in Biohaven clinical studies (but may be considered non-serious AEs):

- A visit to the emergency room or other hospital department <24 hours that does not result in an admission (unless considered "important medical event" or event that is life threatening);
- Elective surgery planned prior to signing consent;
- Admissions as per protocol for a planned medical/surgical procedure;
- Routine health assessment requiring admission (i.e., routine colonoscopy);
- Admission encountered for another life circumstance that carries no bearing on health and requires no medical intervention (i.e., lack of housing, care-giver respite, family circumstances).

Disability/incapacitating: An AE is incapacitating or disabling if the experience results in a substantial and/or permanent disruption of the subject's ability to carry out normal life functions.

8.3.2 Collection and Reporting Serious Adverse Events

Following the subject's written consent to participate in the study, all SAEs, whether related or not related to study drug, must be collected, including those thought to be associated with protocol-specific procedures. All SAEs must be collected that occur from signing consent and throughout the course of the study up to and including the Post-dose Follow-up Visit Day 60.

All SAEs should be followed to resolution or stabilization.

An SAE report should be completed for any event where doubt exists regarding its status of seriousness.

If the investigator believes that an SAE is not related to the study drug but is potentially related to the conditions of the study (such as a withdrawal of previous therapy or a complication related to study procedure), the relationship should be specified in the narrative section of the SAE Report Form.

SAEs, whether related or not related to study drug, overdose (see Section 8.3.3), potential drug induced liver injury (see Section 8.3.3) and pregnancies (see Section 8.3.4) must be reported within 24 hours of the Investigator becoming aware of the event. The Investigator is responsible for submitting all applicable events to the IRB as per the IRB's reporting requirements. Additionally, the Investigator, or designated staff, is responsible for entering the SAE information into the eCRF and/or system (i.e., event term, start/stop dates, causality, and severity).

Any serious adverse event must be reported immediately or no later than 24 hours after awareness of the event to PPD Pharmacovigilance (PVG). A written description of any serious adverse event, using the PPD SAE report form, must be sent to PPD PVG by facsimile (fax), within 24 hours after awareness of the event:

- North America: [name]
- EU EMEA: [contact]

Due to COVID-19 restrictions for sites, SAE reports may be sent via encrypted email to PPD at: [contact]. The subject line of the email must include **"Biohaven Protocol BHV3500-203."**

If a form is unable to be submitted within 24 hours, the SAE may be reported by telephone via the Safety Hotline Number:

- North America: [name]
- EU EMEA: [contact]

If only limited information is initially available, follow-up reports are required. If an ongoing SAE changes in its intensity or relationship to study drug or if new information becomes available, a follow-up SAE report should be sent within 24 hours of the Investigator becoming aware of the updated information using the same procedure used for the transmission of the initial SAE and the same event term should be used.

The minimum information required for an initial SAE report is:

- Sender of report (Site number, Investigator name)
- Subject identification (subject number)
- Protocol number
- SAE term (if an SAE is being reported)

8.3.3 Overdose

An overdose is defined as the accidental or intentional administration of any dose of a product that is considered both **excessive** and **medically important**.

All occurrences of medically significant overdose (suspected or confirmed and irrespective of whether it involved zavegeptant) must be communicated to Biohaven or a specified designee within 24 hours and be fully documented as an SAE. Details of any signs or symptoms and their management should be recorded including details of any treatments administered.

Asymptomatic dosing errors (e.g. accidentally taking two tablets instead of prescribed dose of one tablet in one calendar day) should be reported as deviations.

8.3.4 Pregnancy

If, following the baseline visit, it is subsequently discovered that a study subject is pregnant or may have been pregnant at the time of the investigational product exposure, including during at least 6 half-lives after the product administration, the investigational product will be permanently discontinued in an appropriate manner (i.e., dose tapering if necessary for subject safety). Protocol-required procedures for study discontinuation and follow-up must be performed on the subject unless contraindicated by the pregnancy (i.e., x-ray studies). Other appropriate pregnancy follow-up procedures should be considered if indicated.

Sites should instruct subjects to contact the Investigator if they become pregnant during the course of the study. The investigator must immediately notify the Biohaven (or designee) Medical Monitor and PPD of the event and complete the Pregnancy Form in accordance with SAE reporting procedures as described in Section 8.3.2. The pregnancy should be reported using paper forms, which should be faxed to PPD PVG by facsimile (fax), within 24 hours after Investigator/site awareness of the event:

- North America - [name]
- EU EMEA: [contact]

Due to COVID-19 restrictions for sites, SAE reports may be sent via encrypted email to PPD at: [contact]. The subject line of the email must include **“Biohaven Protocol BHV3500-203.”**

Or if the form cannot be faxed or emailed it should be reported via phone to the PPD Safety Hotline at North America: [name] or EU EMEA: [contact].

Once the paper form is available, the data must be reported per standard procedures.

Follow-up information regarding the course of the pregnancy, including perinatal and neonatal outcome and, where applicable offspring information must also be reported on a Pregnancy Report Form.

Any pregnancy that occurs in a female partner of a male study participant should be reported to the sponsor/PPD. Information on this pregnancy will be collected on the Pregnancy Report Form, as appropriate.

8.3.5 Potential Drug Induced Liver Injury (DILI)

Wherever possible, timely confirmation of the initial liver-related laboratory abnormalities should occur prior to the reporting of a potential DILI event. All occurrences of potential DILIs, meeting the defined criteria, must be reported as SAEs as per Section [8.3.2](#).

Potential drug induced liver injury is defined as:

1. ALT or AST elevation > 3 times the upper limit of normal (ULN)

AND

2. Total bilirubin > 2 times ULN, without initial findings of cholestasis (elevated serum alkaline phosphatase)

AND

3. No other immediately apparent possible causes of ALT or AST elevation and hyperbilirubinemia, including but not limited to, viral hepatitis, pre-existing chronic or acute liver disease, or the administration of other drug(s) known to be hepatotoxic.

If any potential DILI is identified and meets the criteria above, the Biohaven Medical Monitor (or designee) should immediately be contacted for further instruction and whether the subject must discontinue from the trial and appropriate follow up requirements.

8.4 Non-serious Adverse Events

A *non-serious adverse event* is an AE not classified as serious.

8.4.1 Collection and Reporting of Non-Serious Adverse Events

The collection of non-serious AE information should begin at the initiation of study drug through Day 29.

Non-serious adverse events should be followed until conclusion or stabilization or reported as SAEs if they become serious. Follow-up is also required for non-serious AEs that cause interruption or discontinuation of study drug or those that are present at Day 29.

8.4.2 Laboratory Test Abnormalities

The following laboratory test abnormalities should be captured on the non-serious AE eCRF page (out to Day 29) or SAE Report Form (paper or electronic) as appropriate:

- Any laboratory test result that is determined to be clinically significant or meets the definition of an SAE;
- Any laboratory test abnormality that requires the subject to have the study drug discontinued or interrupted;
- Any laboratory test abnormality that requires the subject to receive specific corrective therapy.

8.5 Adverse Events of Special Interest

Not Applicable.

9 STATISTICS

Complete details on the statistical methods for this study may be found in the Statistical Analysis Plan (SAP).

9.1 Sample Size

This study will randomize 120 subjects in a 2 to 1 ratio, to zavegeptant and placebo, respectively.

Since our understanding of the course of the disease as measured by the primary endpoint, and the ability of the drug to alter that course, are limited, the sample size for this study was primarily based on what is typical for a phase II study. Based on a limited set of encountered data, presented below, we believe the study may have roughly 90% power to detect an average improvement of 1 unit on the primary endpoint.

Just prior to the creation of this protocol, some epidemiological data was informally gathered by Biohaven from local hospitals. For 300 subjects tested for COVID-19, the distribution on the primary endpoint was estimated to be as shown in [Table 2](#).

Table 2: Distribution, number (N), and percent (%) of 300 subjects tested for COVID-19

Category	Description	N	%
1	Death	4	1.3%
2	Hospitalized, on invasive mechanical ventilation or ECMO	34	11.3%
3	Hospitalized, on non-invasive ventilation or high flow oxygen devices	30	10.0%
4	Hospitalized, requiring supplemental oxygen	20	6.7%
5	Hospitalized, not requiring supplemental oxygen	14	4.7%
6	Not hospitalized	198	66.0%

The table shows the distribution at the time of initial testing for a broad range of subjects. In this study, the subjects will have tested positive for COVID-19, have been admitted to a hospital, and will generally be in category 4 (hospitalized, requiring supplemental oxygen). The distribution of subjects after 14 days of treatment with either zavegeptant or placebo is a matter of speculation. However, it does seem reasonable to discount the large number of subjects in category 6 (not hospitalized). These subjects, who were tested and sent home, would not be admitted into this study. If the category 6 subjects are not included in the calculations, then the distribution of the remaining data can be described as having a mean of 3.1 and a standard deviation of 1.1.

Based on the table, we speculate that after 14 days of treatment the distribution of subjects on placebo might have a standard deviation as high as 1.5 units. If zavegeptant improves the response of subjects by an average of 1 unit over placebo, then this study will have roughly 90% power. This calculation is based on a t-test, with sample sizes of 80 and 40 per group, and alpha level of 0.05 and a common standard deviation of 1.5 units.

9.2 Analysis Sets

The following analysis sets will be used in this this study:

- Enrolled: Subjects who sign informed consent and are assigned a subject identification number
- Randomized: Subjects in the enrolled analysis set who receive a randomized treatment group assignment (zavegeptant or placebo)
- Safety: Subjects in the enrolled analysis set who receive at least one dose of study drug (zavegeptant or placebo)
- Efficacy: Subjects in the randomized analysis set who are randomized only once, and receive at least one dose of study drug.

9.3 Statistical Methods

Categorical variables are tabulated with counts and percentages. Continuous variables are summarized with univariate statistics (e.g., n, mean, standard error, median, minimum and maximum).

For the calculation of descriptive statistics of observed data, subjects must have a baseline value to be evaluable for endpoints based on values and changes from baseline over time.

Tabulations of the following endpoints present the number of unique subjects with an event: protocol deviations; non-study medications; AEs; and laboratory test abnormalities. Thus, for these endpoints, multiple occurrences of the same event are counted only once per subject.

9.3.1 Demographic and Baseline Characteristics

Tabulations of demographic and baseline characteristics are made for the efficacy and safety analysis sets.

9.3.2 Primary Endpoint

The primary endpoint will be analyzed using a Mixed Model for Repeated Measures (MMRM) with treatment group, visit, visit-by-treatment group interaction, and randomization stratum age group as fixed effects, baseline SpO₂/FiO₂ ratio as a covariate, and subject as a random effect. Visit will be a categorical variable based on analysis visit windows for Days 5, 10, 15, 22, and

29. The primary endpoint will be tested by comparing zavegeptant to placebo at Day 15 at an alpha level of 0.05. Descriptive statistics will be provided for each treatment group that show the number and percentage of subjects in each category. Analyses are based on the efficacy analysis set.

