3 STUDY ENDPOINTS

3.1 Primary Endpoint

Efficacy will be measured by the difference between treatment groups in the mean 6-point severity rating at Day 15. The severity ratings are:

1. Death
2. Hospitalized, on invasive mechanical ventilation or ECMO
3. Hospitalized, on non-invasive ventilation or high flow oxygen devices
4. Hospitalized, requiring supplemental oxygen
5. Hospitalized, not requiring supplemental oxygen
6. Not hospitalized

Six point severity ratings are from the 6-point ordinal rating scale eCRFs. Deaths through Day 15 from AE/SAE and subject disposition CRFs are also taken into account.

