4 STUDY PLAN

4.1 Study Design and Duration

This is a double-blind, randomized, multicenter, inpatient (and post-discharge outpatient) evaluation of the safety and efficacy of zavegeptant (BHV-3500) as compared to placebo in the treatment of COVID-19-associated pulmonary disease. The study drug will be zavegeptant or matching placebo, given as 10 mg IN dose every 8 hours (+/- 2 hours) for approximately 14 days (42 doses). The study will randomize approximately 120 subjects in a 2:1 ratio across the two treatment groups (zavegeptant or matching placebo). The randomization will be stratified by age (less than 60 years vs 60 years and older).

After signing informed consent and meeting eligibility criteria, the subject may be immediately randomized and dosed with the double-blind study medication (10 mg or matching placebo) and continue dosing every 8 hours (Q8h +/- 2 hours) up to approximately 14 days (42 doses).

[figure not shown]
For the purposes of this protocol, the start of Visit Day 1 will start when the 1st dose of study drug is administered until 24 hours later. Therefore, depending on the time when the 1st dose of study drug is administered, a visit day may spread over 2 calendar days. The last dose of study drug could be administered on Visit Day 14 but could actually occur on calendar day 15 of the study. The EOT or Day 15 assessments (depending on when subject stops study drug) should be completed after the last dose of study drug, and the subjects should remain in the hospital for a full 24 hours after their last dose of drug if they are to be released.

Randomization will be done through an IWRS that will be accessed by the unblinded research pharmacists or their designees. so that subjects can be dosed as soon as possible following consent and assessment of eligibility criteria. After completion of treatment, subjects will be followed out to Day 60 (+/- 15 days) during the post treatment phase.

This study has a duration approximately 8 weeks from time of Screening and obtaining consent through the Post-Dose Follow-up Visit (Day 60 +/- 15 days).

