							
within 48 hours of signing Informed Consent may be used as the Screening assessment. While subjects are in the hospital, vital signs will be collected once daily in the AM or PM but around the same time every day within 3 hours and entered on the eCRF.
 
After hospital discharge, vital signs should be collected at in-person visits on Days 22, 29, and 60 (if this is an in-person visit).

SpO2 and FiO2	X	X	X	X	X	X	
SpO2 and FiO2 collected as part of SOC within 48 hours of signing Informed Consent may be used as the Screening assessments. While the subject is in the hospital, this is collected in the eCRF once daily and should correlate (AM or PM) with the time the vital signs and the NEWS2 are collected.
 
After hospital discharge, SpO2 and FiO2 should be collected at any in-person visits on Days 22, 29, and 60 (if this is an in-person visit).

Procedure	Screening Visit Day -2 to Day 1	Baseline Visit (Randomization) Day 1	Days 2 through 14 (+/- 1 day)¹	End of Treatment (EOT) Visit or Day 15 (+/- 1 day)²	Post-Treatment Phase Days 16 (+/- 1 day) through Day 29³ (+/- 2 days)	Day 60 (+/- 15 days)	Comments
Arterial Blood Gas (ABG)							Arterial Blood Gas (ABG) is not a required assessment for the protocol. However, if it is collected as per SOC within 48 hours from signing Informed Consent through Day 29, this data should be entered in the eCRF in Unscheduled Visit ABG pages.
6-point ordinal scale	X	X	X	X	X	X	While in the hospital, this is collected once daily. This may be collected in the AM or PM at the discretion of the Investigator or staff but should be collect around the same time (within 3 hours) every day. If subjects are discharged from the hospital and unable to return for in-person visits, this scale should be assessed by phone on Days 15, 22, and 29. After hospital discharge, this assessment should be collected at in-person visits on Days 22, 29, and 60 (if an in-person visit).

Procedure	Screening Visit Day -2 to Day 1	Baseline Visit (Randomization) Day 1	Days 2 through 14 (+/- 1 day)¹	End of Treatment (EOT) Visit or Day 15 (+/- 1 day)²	Post-Treatment Phase Days 16 (+/- 1 day) through Day 29³ (+/- 2 days)	Day 60 (+/- 15 days)	Comments

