5.2 Inclusion Criteria

1. Subjects must provide informed consent in accordance with requirements of the study center's IRB or ethics committee, prior to the initiation of any protocol-required procedures.
2. Subjects must agree to provide all requested demographic information (i.e. gender, race).
3. Subjects must be able to read and understand English or Spanish.
4. Subjects must be over the age of 18 years.
5. Subjects must have laboratory-confirmed SARS-CoV-2 infection as determined by PCR-based commercial or public health assay.
6. Subjects must have symptoms that require hospitalization with supplemental oxygen and/or non-invasive ventilation as determined by the admitting physician. The maximum nasal cannula O₂ concentration should be determined by the treating clinician and the limitations of the specific equipment.
7. Subjects must be willing and able to comply with study-related procedures/assessments.

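### The primary MMRM leaves out the pre-dose 6-point rating, which is already collected and can be 3 or 4 at entry; adding it is a cheap, optional gain in precision

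*Protocol*

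**What the plan says.** Section 9.3.2 lists the terms of the primary model: treatment group, visit, visit-by-treatment interaction, and "randomization stratum age group as fixed effects, baseline SpO₂/FiO₂ ratio as a covariate, and subject as a random effect". The modelled visits are Days 5, 10, 15, 22 and 29, so the entry rating is not in the model as a response either.

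The 6-point row of Table 1 (section 4.3) is marked at both Screening and Baseline, and the comment adds: "While in the hospital, this is collected once daily".

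Two entry ratings are possible. Inclusion criterion 6 (section 5.2) reads "Subjects must have symptoms that require hospitalization with supplemental oxygen and/or non-invasive ventilation as determined by the admitting physician", and continues: "The maximum nasal cannula O₂ concentration should be determined by the treating clinician and the limitations of the specific equipment". Section 3.1 defines rating 3 as "Hospitalized, on non-invasive ventilation or high flow oxygen devices"; rating 4 is supplemental oxygen. Randomization is stratified by age group only (section 4.1).

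On the expected entry mix, section 9.1 says that subjects "will generally be in category 4 (hospitalized, requiring supplemental oxygen". No percentage is given.

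**The concern.** The baseline value of the outcome is usually the first covariate one considers in a repeated-measures model. Here it is on the case report form but not in the model. Subjects one category apart on the primary scale can both be randomized, and with 80 against 40 subjects and no stratification on severity their balance is left to chance.

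SpO2/FiO2 is related to the rating but is not the same thing. The rating records the mode of respiratory support, which is what the endpoint scores. If it predicts the Day 15 rating beyond SpO2/FiO2, leaving it out makes the confidence interval for the Day 15 difference slightly wider than it need be.

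**Working it through.** **1. The plan's own power.** Inputs from section 9.1: 80 and 40 subjects, difference 1 unit, common SD 1.5, alpha 0.05, t-test. Two-sided testing is assumed, because sidedness is not stated. SE = 1.5 × √(1/80 + 1/40) = 0.2905; noncentrality = 1/0.2905 = 3.443; 118 df. Power is 92.7%, against the stated roughly 90%, so there is no shortfall.

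**2. What the document offers on the entry mix.** Table 2 counts 30 people in category 3 and 20 in category 4 at initial testing: 30/(30 + 20) = 60% at rating 3 among those two categories. Section 9.1 expects study subjects mostly in category 4. Shares of 2%, 10%, 30% and 60% are therefore all shown; 2%, 10% and 30% are illustrative.

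**3. Assumptions not in the documents.** Day 15 gap between entry ratings g = 1 unit; correlation of rating with SpO2/FiO2 r = 0.3 to 0.7; share f of the gap that runs through SpO2/FiO2 itself = 0, 0.5 or 1. Within-arm variance is 1.5² = 2.25, and p is the share at rating 3.

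**4. Formulas (Day 15 ANCOVA approximation).**
- Residual variance with SpO2/FiO2 in the model: V1 = 2.25 − p(1−p)g²(f/r + (1−f)r)²
- Further reduction from adding the rating: D = (1−f)² p(1−p) g² (1−r²)
- Gross cut = D/V1
- Net cut = 1 − (1 − D/V1) × 115/114. The factor 115/114 is the expected variance inflation from one more covariate at n = 120, about 0.9%.

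**5. Worked example, p = 0.10, r = 0.5.**
- f = 0: V1 = 2.25 − 0.09 × 0.25 = 2.2275; D = 0.09 × 0.75 = 0.0675; gross 3.0%, net 2.2%.
- f = 0.5: V1 = 2.25 − 0.09 × 1.25² = 2.1094; D = 0.25 × 0.0675 = 0.0169; gross 0.8%, net −0.1%.
- f = 1: D = 0; net −0.9%.

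**6. Ranges over r and f.** A negative net cut means that variance rises. Power is by noncentral t for a 1-unit effect, comparing V1 with V1 × (1 − net cut).

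| Share at rating 3 | Net variance cut | Net power change (points) |
|---|---|---|
| 2% | −0.9% to −0.1% | −0.2 to about 0 |
| 10% | −0.9% to +2.8% | −0.2 to +0.65 |
| 30% | −0.9% to +7.8% | −0.1 to +1.7 |
| 60% (Table 2 ratio) | −0.9% to +9.0% | −0.1 to +2.0 |

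Each upper end is at f = 0 and r = 0.3. For example, at 60%: V1 = 2.25 − 0.24 × 0.09 = 2.2284; D = 0.24 × 0.91 = 0.2184; gross 9.8%, net 9.0%. With f = 0, SpO2/FiO2 predicts Day 15 only through the rating, so these are upper limits. Half-way (f = 0.5, r = 0.5), the net cut is −0.1%, +1.2% and +1.5% at 10%, 30% and 60%.

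Cells with f = 1 and r = 0.3 at 30% and 60% are removed, because the implied V1 is negative (2.25 − 0.21/0.09 = −0.083 and 2.25 − 0.24/0.09 = −0.417). No bound changes, since f = 1 gives −0.9% at the other correlations.

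**7. Checks.** A Day 15 ANCOVA simulation (100,000 replicates, r = 0.5, age stratum included) gave net cuts of 2.1%, −0.2% and −0.9% at p = 0.10 for f = 0, 0.5 and 1 (formula 2.2, −0.1, −0.9). At p = 0.30 it gave 6.6%, 1.1% and −0.9% (formula 6.4, 1.2, −0.9). A separate grid took 1.5 as the residual SD, 5% to 50% at rating 3 and a gap of 0.25 to 1 unit. Power there went from 92.3% to between 92.1% and 94.7%, a change of −0.2 to +2.4 points.

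**The case against.** The strongest reply is that nothing here is an error. The sponsor pre-specified a continuous measure of baseline respiratory severity, and SpO2/FiO2 both tracks oxygen support and grades subjects within rating 4. If entrants are nearly all in category 4, the rating is almost constant. At 2% in category 3 every net figure is zero or a loss. Section 5.4 also speaks of ventilation, invasive or not, as something a subject progresses to after randomization. Every driver of the gain is assumed, and the calculation is a Day 15 ANCOVA rather than the MMRM. One coefficient pooled over five visits would gain less at Day 15 if the effect of the entry rating varies over time.

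Most of this stands, and it is why the point is optional. It does not remove the point. Section 9.1 says only that entrants are generally in category 4, criterion 6 expressly admits non-invasive ventilation, and Table 2 has more people in category 3 than in category 4. A share well above 2% to 10% is therefore not excluded, and the worst case is trivial.

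Two stronger readings are tempting and are not supported. A reader might infer that omitting the baseline outcome biases the comparison or leaves the trial underpowered. Randomization keeps the unadjusted-for-rating comparison valid, and the stated inputs give 92.7%. A reader might also take Table 2 as a forecast that 60% will enter at rating 3. The table describes people tested for COVID-19 at the time of initial testing, and section 9.1 itself separates them from the study's entrants; 60% is one end of a range.

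**Conclusion.** The point holds as a cheap improvement in precision and nothing more. The net effect on the variance of the Day 15 difference lies between a 0.9% increase and a reduction of 2.8%, 7.8% or 9.0% at 10%, 30% or 60% entering at rating 3, worth at most about 2 points of power. These figures rest on SD 1.5, a 1-unit Day 15 gap, a correlation with SpO2/FiO2 of 0.3 to 0.7, and the Day 15 approximation. The protocol gives neither the entry mix nor the prognostic value of the rating. The addition pays off only if the rating removes more than about 0.9% of residual variance beyond SpO2/FiO2. The SAP was not available for this check; if it already carries the term, the point is settled.

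**What to change.** In section 9.3.2, add the last 6-point rating before the first dose as a covariate, keeping age group and SpO2/FiO2, and fix this before unblinding. Define the rating in one line, because section 4.1 says "the start of Visit Day 1 will start when the 1st dose of study drug is administered until 24 hours later": a rating labelled Day 1 may have been taken after dosing, and the Screening rating should then be used.

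The costing above is for a single main effect; it does not settle whether a rating-by-visit term would be worth its extra coefficients. The blinded, pooled entry mix would show whether the covariate can matter.

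The cost is one covariate and one sentence, with no new data, and about 0.9% of variance at n = 120 if the rating proves uninformative. If the sponsor expects almost all subjects at rating 4, leaving the model as it is loses nothing.
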